Efficacy Endpoints	
Overall response rate (ORR) ORR is defined as sum of CR and PR rates.
 
Complete Response (CR) Rate CR rate is defined as the proportion of subjects who achieve a CR.
 
Progression-free survival (PFS) PFS is defined as the interval from enrollment to the earlier of the first documentation of definitive disease progression or death from any cause. Definitive disease progression based on standard criteria (Hallek et al. 2008) and occurring for any reason (i.e., increasing lymphadenopathy, organomegaly or bone marrow involvement; decreasing platelet count, hemoglobin, or neutrophil count; or worsening of disease-related symptoms) other than lymphocytosis.
 
Minimal Residual Disease (MRD) Negativity Rate MRD negativity rate is defined as the proportion of subjects who are MRD negative.
 
Duration of response (DOR) DOR is defined as the interval from the first documentation of CR or PR to the earlier of the first documentation of definitive disease progression or death from any cause.

Safety Endpoints	All AEs will be reported and evaluated using National Cancer Institute's Common Terminology Criteria (CTCAE) v4.0.
Study Design	
This study is intended to serve as a compassionate use study to allow subjects who have previously progressed on Arms B, C & D in the parent trial UTX-TGR-304 to receive ublituximab plus TGR-1202. Those subjects must have had confirmed disease progression by the independent radiology committee (IRC). Additionally, at the termination of study UTX-TGR-304, non-progressed subjects from Treatment Arm A may be enrolled to this study.
 
Subjects from Treatment Arms B, C, and D may start treatment with ublituximab + TGR-1202, while subjects entering this study from Treatment Arm A may continue their treatment until they show disease progression, are unable to continue treatment for any reason such as lack of tolerability, or until the treatment is commercially available.

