	
During the study period, all subjects will be evaluated for response by CT and/or MRI. Evaluations are to be obtained at approximately cycles 3, 6, and 12. Following cycle 12, evaluations should occur at least every 12 cycles unless clinically indicated sooner. Subjects followed for PFS off treatment should have scans completed per institutions standard of care and reported in the EDC until progressive disease or subject begins another anti-cancer treatment. Date of progression, beginning of new treatment, and/or death should be entered in the eCRF. Subjects should remain on study treatment until the occurrence of definitive disease progression, unacceptable toxicity, or withdrawal from the study due to investigator discretion or other reasons. Subjects who discontinue from study treatment and have not progressed should continue to be followed for progression.
																								

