### 4.1 OVERVIEW OF STUDY DESIGN

---

This Companion Study is intended for subjects who previously enrolled to the parent trial [UTX-TGR-304](#). Subjects from Treatment Arms B, C, and D with disease progression confirmed by the independent review committee (IRC), may be enrolled into this Companion Study. At the end of the UTX-TGR-304 study, non-progressed subjects from Treatment Arm A may also be enrolled to this Companion Study. Subjects from Treatment Arms B, C, and D may start treatment with ublituximab + TGR-1202, while subjects entering the Companion Study from Treatment Arm A may continue their treatment as specified by this protocol. All subjects enrolled to the Companion Study should receive ublituximab in combination with TGR-1202 (at the same dose and schedule as the Treatment Arm A in UTX-TGR-304) until they show disease progression, are unable to continue treatment for any reason such as lack of tolerability, or until the treatment is commercially available.

During the study period, all subjects will be evaluated for response by CT and/or MRI. Evaluations are to be obtained at approximately cycles 3, 6 and 12. Following cycle 12, evaluations should occur at least every 12 cycles unless clinically indicated more frequently. Subjects should remain on study treatment until the occurrence of definitive disease progression, unacceptable toxicity, or withdrawal from the study due to investigator decision or other reasons. Subjects who discontinue from study treatment (either for toxicity or physician choice) and have not progressed should continue to be followed for progression per institutional standard of care and reported in eCRF. Date of progression, beginning of new treatment, and/or death should be entered in the eCRF.

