### 4.4 DISCONTINUATION FROM STUDY TREATMENT

---

Subjects will be discontinued from study treatment for any of the following reasons:

- Disease progression
- Intolerable toxicity related to study drug
- Subject requests to withdraw consent or discontinue treatment
- Pregnancy
- Inability of the subject to comply with study requirements
- Conditions requiring therapeutic intervention not permitted by the protocol
- Non-compliance/lost to follow-up
- Investigator discretion
- Discontinuation of the study by the Sponsor

Subjects who discontinue from study treatment (for reasons other than progressive disease) should continue to be followed for progression.

Subjects who discontinue all study treatment but remain on study for disease progression assessment will have an End of Treatment (EOT) visit and will continue to be followed for adverse events (treatment-related AEs and disease-related AEs), disease progression and other protocol required procedures (see [Section 5, Table 2](#) for EOT and follow up assessment schedule). All new treatment-related AEs occurring within 30 calendar days from treatment discontinuation must be reported and followed until resolution, unless, in the opinion of the investigator, these events are not likely to improve because of the underlying disease. In this case the investigators must record the reason for not conducting the 30-day safety evaluation in the subject's medical records and as a comment on the electronic Case Report Form (eCRF).

All subjects who have CTCAE Grade 3 or 4 laboratory abnormalities at the time of withdrawal should be followed until the laboratory values have returned to Grade 1 or 2, unless in the opinion of the investigator, it is not likely that these values are to improve because of the underlying disease. In this case, the investigator must record his or her reasoning for making this decision in the subject's medical records and as a comment on the eCRF.

Subjects who discontinue from the study will have an End of Study visit (EOS - see [Section 5, Table 2](#))

No formal futility analysis of efficacy or safety will be conducted in this study, however if [Study 304](#) is closed for futility for either safety or efficacy reasons, then this Study UTX-TGR-204 will also be terminated.

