## 9.8.2 SECONDARY EFFICACY VARIABLES

---

Progression free survival (PFS) is defined as the time from study entry to the first documentation of tumor progression or death due to any cause whichever comes first. For subjects previously on Arm A of Study UTX-TGR-304, PFS will be calculated from the date of randomization on Study UTX-TGR-304 to the first documentation of tumor progression or death due to any cause whichever comes first. This variable will be analyzed via Kaplan-Meier methodology. The median PFS will be estimated by treatment group, if appropriate (i.e., if sample sizes are sufficient) and overall.

MRD negativity rate is defined as the proportion of subjects who are MRD negative. This variable will be analyzed by the total number and percentage of subjects who are confirmed to achieve MRD negativity as per laboratory confirmation by treatment group and overall.

Duration of response is defined as the time from documentation of a response to treatment to the first documentation of tumor progression or death due to any cause whichever comes first. For subjects previously on Arm A of Study UTX-TGR-304, unless the subject's best overall response during study UTX-TGR-304 was stable disease, the duration of response will be determined from the first documented response on Study UTX-TGR-304. Duration of the response will be summarized using n (sample size), mean, standard deviation, median, minimum and maximum for the responders by treatment group and overall.

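### Duration of response is a time-to-event variable, but Section 9.8.2 summarizes it by plain mean and median with no rule for responders who have had no event

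*Combined protocol and SAP*

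**What the plan says.** The synopsis (Efficacy Endpoints) states: "DOR is defined as the interval from the first documentation of CR or PR", ending at definitive progression or death from any cause. Sections 2.2 and 9.8.2 define the variable in the same way. For the analysis, Section 9.8.2 says: "Duration of the response will be summarized using n (sample size), mean, standard deviation, median, minimum and maximum for the responders". This is planned for each prior arm and for all arms pooled. For PFS, which ends at the same two events, the same section says: "This variable will be analyzed via Kaplan-Meier methodology".

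No section gives a censoring rule for DOR, and none gives one for PFS.

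On follow-up, the synopsis (Study Design) has off-treatment scans "reported in the EDC until progressive disease or subject begins another anti-cancer treatment". Section 5, Table 2 places the end-of-study visit at progression or the start of non-protocol therapy. Section 4.4 ends this study if Study 304 closes for futility.

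For former Arm A subjects, Section 9.8.2 starts PFS at randomization on Study 304. It starts DOR at the first response there, unless the best response on Study 304 was stable disease. Section 3.1 admits Arm A subjects only if they have not progressed.

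**The concern.** A responder who has neither progressed nor died has no DOR under the definition; all that is known is that the response lasted at least until the last assessment. A plain mean or median needs a number for that subject. The programmer must either enter the follow-up time as though the response had ended, or drop the subject. The plan does not say which, and the two choices give different answers.

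For Arms B, C and D both choices push the estimate down. The observed time is the smaller of the true duration and the follow-up, so its mean cannot exceed the true mean. If only subjects with events are kept, and censoring is independent of duration, longer responses are less likely to be kept. The reported DOR would then partly measure how long responders were followed.

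What is at stake is the accuracy of a reported estimate. Section 9.8.2 lists DOR as secondary; only the synopsis makes it primary, and only for former Arm A subjects.

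**Working it through.** **No figure to reproduce.** The documents give no expected DOR, follow-up time, event count or censoring rate. All inputs to steps 1 to 3 are therefore assumptions.

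**1. Worked example for Arms B, C and D.** DOR (D) is exponential with true median m = 18 months. Follow-up after response (C) is independent and uniform from 12 to 36 months.

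- Hazard: λ = ln 2 / m = 0.6931 / 18 = 0.03851 per month.
- Share without an event: p = (e^(−12λ) − e^(−36λ)) / (24λ) = (0.6300 − 0.2500) / 0.9242 = 0.411.
- Plain mean, follow-up counted as the end of response: E[min(D, C)] = (1 − p)/λ. Ratio to the true mean 1/λ: 1 − 0.411 = 0.59.
- Plain median: solve e^(−λt) × (36 − t)/24 = 0.5. At t = 14.79, 0.5658 × 0.8838 = 0.500. Ratio 14.79/18 = 0.82.
- Events-only median: solve 1 − e^(−λt) = (1 − p)/2 = 0.2944, so t = 0.3488/0.03851 = 9.06. Ratio 9.06/18 = 0.50.
- Kaplan-Meier: the survival curve reaches 0.5 at 18 months, inside the follow-up range. Ratio 1.00.

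**2. How far this depends on the assumptions.** Follow-up 12 to 36 months, ratios to truth:

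| True median (months) | No event | Plain median | Plain mean | Events-only median | Kaplan-Meier median |
|---|---|---|---|---|---|
| 12 | 27% | 1.00 | 0.73 | 0.65 | 1.00 |
| 18 | 41% | 0.82 | 0.59 | 0.50 | 1.00 |
| 24 | 51% | 0.69 | 0.49 | 0.41 | 1.00 |

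- Follow-up 24 to 36 months: everyone is followed to or past the true median, so the plain median is unbiased. The plain mean is still 0.82, 0.68 and 0.58 of truth for true medians of 12, 18 and 24 months.
- Follow-up 0 to 36 months, true median 18: 54% have no event and the plain median is 0.54 of truth.
- Follow-up 6 to 36 months, true median 24 (56% without an event): plain median 13.7 months, events-only median 8.7, Kaplan-Meier 24.0.
- Follow-up 3 to 24 months, true median 24 (69% without an event): the Kaplan-Meier median is not reached, while the plain median is 10.0 months.

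**3. Why ordinary Kaplan-Meier is not enough for Arm A.** The clock starts on Study 304, but anyone who progressed before entry is absent. Counting the remaining subjects as at risk from time zero gives them time in which they could not have had an event (left truncation).

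- DOR was simulated with true medians of 12, 18 and 24 months, entry starting 0.5, 6 or 12 months after response, and follow-up of 0 to 12 or 0 to 24 months. Ordinary Kaplan-Meier gave about 1.5 to 3.2 times the unconditional median, where a median was reached.
- PFS was simulated with true medians of 18 to 36 months and entry starting 6, 12 or 18 months after randomization. The planned Kaplan-Meier gave about 1.6 to 2.8 times truth, where a median was reached.
- With delayed entry the target is the median given survival to the earliest entry time e. For exponential durations this is e + m. With m = 18 and e = 6 that is 24 months, or 24/18 = 1.33 times the unconditional median. Delayed entry recovers this conditional target, not the unconditional median.

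**4. Why the censoring date must be written down.** The synopsis says: "Following cycle 12, evaluations should occur at least every 12 cycles unless clinically indicated sooner". Twelve cycles of 28 days are 336 days, about 11 months. The last scan and the last contact can therefore differ by most of a year.

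**The case against.** The strongest reply has four parts.

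- **The study is descriptive.** It is a compassionate-use extension with no hypothesis test, and no sample size or stopping decision uses DOR. This stands and limits the severity. It does not excuse the method, because estimates are the study's only efficacy output.
- **Follow-up may be long.** The synopsis keeps the study open while subjects are enrolling in, or have been enrolled to, Study 304. A reader might also take "or until the treatment is commercially available" (Section 4.1) and "Non-compliance/lost to follow-up" (Section 4.4) as points at which response follow-up stops. The documents do not support that: both are reasons for ending treatment, and subjects who stop without progression should still be followed for progression. The cut-offs stated directly are new anti-cancer therapy and study termination. Those are enough to make event-free responders foreseeable, but not to say how many there will be.
- **The size is assumed.** This also stands. The plain-median bias runs from none to about half of truth across the scenarios above, and the documents cannot say which applies.
- **An analyst would use Kaplan-Meier anyway.** The section names Kaplan-Meier for PFS and prescribes something else for DOR, so the written instruction points the other way. PFS is not a complete model either, since it too lacks a censoring rule and its Arm A clock has the truncation problem.

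**Conclusion.** The point holds. The stated summary does not suit the stated definition, and following it gives a mean DOR that is biased low for Arms B, C and D. The median is usually low too; the exception is the plain median that counts follow-up as complete, when every responder is followed to or past the true median. The illustration (0.82, 0.59 and 0.50 of truth) rests on exponential durations, independent censoring and assumed follow-up. It shows direction and plausible scale and does not predict this study's results.

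Two stronger readings should be resisted. A reader might infer that a trial conclusion or error rate is affected, but no test or decision uses DOR. A reader might also infer that Arm A DOR will be understated, or that ordinary Kaplan-Meier would repair it. Censoring pulls Arm A estimates down and left truncation pushes them up, so the direction of the plain summary is not determined, and ordinary Kaplan-Meier overstates the unconditional median.

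This should be fixed: the method is wrong as written and the repair is cheap.

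**What to change.** In Section 9.8.2, replace the DOR summary sentence with:

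> DOR will be estimated in responders by the Kaplan-Meier method. Responders without progression or death are censored at the last disease assessment, and those starting new anti-cancer therapy before progression at the last assessment before it. Numbers of responders, events and censored subjects and the median with a 95% confidence interval are reported by prior Study 304 arm and for Arms B–D combined.

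Drop the mean and SD, and apply the same censoring rule to PFS. Add for Arm A:

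> Where the DOR or PFS clock starts on Study 304, Arm A is not pooled with the other arms; subjects enter the risk set at enrollment in this study, numbers at risk are shown, and results are labelled as conditional on being event-free at entry.

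Arm A subjects who first respond in this study need no delayed entry for DOR. A sensitivity analysis counting new therapy as an event is optional; it would address possible informative censoring.

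The cost is text in one section. Section 4.1 already requires the dates: "Date of progression, beginning of new treatment, and/or death should be entered in the eCRF". Section 9.8.2 already relies on the Study 304 randomization and response dates. The downsides are that some medians may be not reached, that the Arm A curve rests on few subjects at early times, and that the planned overall figure gives way to a combined figure for Arms B–D with Arm A alongside.

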## 10 SAFETY REPORTING AND ANALYSIS

---

### 10.1 SAFETY ANALYSES

---

Safety evaluations will be based on the incidence, intensity, and type of adverse events, as well as on clinically significant changes in the subject's physical examination, vital signs, and clinical laboratory results. Safety analyses will be performed using the safety population. Safety variables will be tabulated and presented by the dose of the combination of ublituximab + umbralisib study drug actually received. Exposure to study treatment and reasons for discontinuation of study treatment will also be tabulated by treatment group and overall.

### 10.2 ADVERSE EVENT CHARACTERISTICS

---

**CTCAE term (AE description) and grade:** The descriptions and grading scales found in the revised NCI Common Terminology Criteria for Adverse Events (CTCAE) version 4.0 will be utilized for AE reporting. All appropriate treatment areas should have access to a copy of the CTCAE version 4.0. A copy of the CTCAE version 4.0 can be downloaded from the CTEP web site [http://ctep.cancer.gov/protocolDevelopment/electronic\\_applications/ctc.htm](http://ctep.cancer.gov/protocolDevelopment/electronic_applications/ctc.htm).

**'Expectedness':** AEs can be 'Unexpected' or 'Expected' for expedited reporting purposes only. Expected AEs are defined as those described in the ublituximab Investigator Brochure and the umbralisib Investigator Brochure.

### 10.3 DEFINITIONS OF ADVERSE EVENTS

---

An adverse event (AE) is any untoward medical occurrence in a subject or clinical investigation subject administered a pharmaceutical product. An AE does not necessarily have to have a causal relationship with this treatment. An adverse event (AE) can therefore be any unfavorable and unintended sign (including an abnormal laboratory finding, for example), symptom, or disease temporarily associated with the use of a medicinal product, whether or not considered related to the medicinal product. This includes any occurrence that is new in onset or aggravated in severity or frequency from the baseline condition.

In clinical studies, an AE can include an undesirable medical condition occurring at any time, including run-in or washout periods, even if no study treatment has been administered. The NCI Common Terminology Criteria for Adverse Events (CTCAE) v4.0 is to be used for the grading of severity of symptoms and abnormal findings. For adverse events not covered by the NCI-CTCAE Version 4.0 grading system, the following definitions will be used:

- **Grade 1:** Mild; asymptomatic or mild symptoms; clinical or diagnostic observations only; intervention not indicated.
- **Grade 2:** Moderate; minimal, local or non-invasive intervention indicated.
- **Grade 3:** Severe or medically significant but not immediately life-threatening; hospitalization or prolongation of hospitalization indicated.
- **Grade 4:** Life-threatening consequences; urgent intervention indicated.
- **Grade 5:** Death related to AE.

## 10.4 ADVERSE EVENTS (AE'S) AND TREATMENT EMERGENT ADVERSE EVENTS (TEAE'S)

---

All AEs and SAEs occurring on study will be listed by subject. The frequency and percentages of subjects with treatment-emergent adverse events (TEAEs) will be tabulated by system organ class (SOC) and preferred term (PT), where treatment-emergent is defined as any AE that:

- Occurs after first dosing of study medication and through the end of the study or up through 30 days after the last dose of study treatment, or
- Is considered treatment-related regardless of the start date of the event, or
- Is present before first dosing of study medication but worsens in intensity or the investigator subsequently considers treatment-related.

TEAEs that are considered at least possibly related to study treatment will be tabulated as well as deaths, SAEs, and events resulting in treatment discontinuation.

AEs that occur after informed consent but before first dosing of study medication will not be summarized but will be listed.

At each level of summarization, a subject will be counted only once for each AE, SOC, or PT experienced within that level. In the summation for AE severity, within each level of AE, SOC, or PT experienced, the one with the highest severity will be included. In the summation for AE's relationship to the study drug, within each level of AE, SOC, or PT experienced, the one with the closest relationship to the study drug will be included.

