#### Treatment Schema for Subjects Crossing over from Arm A:

Subjects who crossover from Treatment Arm A will continue their treatment where they left off at the termination of [protocol UTX-TGR-304](#).

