### 9.3 ANALYSIS POPULATIONS

---

The Intent-to-Treat (ITT) population will consist of all subjects who were enrolled and have at least one post-treatment efficacy measurement. Primary efficacy analyses will be performed based on the ITT population.

The Safety Population will include all subjects who were enrolled and received at least one dose of study drug. All safety assessments including toxicity will be performed on the Safety Population.

The Per-Protocol Population (PP) will consist of all ITT subjects without a major protocol deviation. The criteria for a major protocol deviation will be determined and documented prior to data base lock. Subject exclusion from the PP population will also be determined and documented prior to database lock. Supportive analyses may be performed based on the PP population.

Furthermore, in the analyses/summaries, subjects will be assigned a treatment group based on the treatment they received on study UTX-TGR-304 prior to their entering of this Companion Study as appropriate.

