## 9.7 EXTENT OF EXPOSURE

---

The dose (mg) of study drugs administered, the total number of doses of study drugs, and the duration of treatment (number of study cycles) will be summarized with descriptive statistics. The number and percentage of subjects whose dose is modified at any time will be summarized by each type of modification by cycle and overall. The proportion of subjects completing each cycle of treatment will be summarized.

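### TEAEs are planned only as crude subject percentages, with no firm rule separating Arm A (continuing the combination) from Arms B, C and D (starting it), so group figures are not comparable and a pooled figure depends on cohort mix

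*Combined protocol and SAP*

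**What the plan says.** **Measure.** Section 10.4: "The frequency and percentages of subjects with treatment-emergent adverse events (TEAEs) will be tabulated" by system organ class and preferred term. Under its counting rule, "a subject will be counted only once for each AE, SOC, or PT experienced within that level". Related TEAEs, deaths, SAEs and events leading to discontinuation are also tabulated. No person-time rate, cumulative incidence or time-window summary is specified for adverse events.

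**Time at risk.** The TEAE window runs from first dosing "through the end of the study or up through 30 days after the last dose of study treatment". Section 4.1 continues treatment until subjects progress, "are unable to continue treatment for any reason such as lack of tolerability, or until the treatment is commercially available". The synopsis sets no fixed study length.

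**Who enters.** Under Section 3.1, subjects from B, C and D enter after confirmed progression, and Arm A subjects enter without progression once the parent study is complete. Section 6.1 says that Arm A subjects "will continue their treatment where they left off at the termination of" the parent protocol. Section 4.1 has B, C and D start the combination here.

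**Grouping.** Section 9.3: "subjects will be assigned a treatment group based on the treatment they received on study UTX-TGR-304", qualified by 'as appropriate'. The synopsis says only that safety 'may' be shown that way and overall. Section 10.1 instead presents safety variables by the dose of the combination each subject in fact received.

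**Exposure.** Section 9.7: "the duration of treatment (number of study cycles) will be summarized with descriptive statistics". Section 10.1 tabulates exposure by group and overall. Neither section uses exposure as a denominator for adverse events.

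**The concern.** A crude percentage answers how many subjects had the event over the time each was observed. Comparing two such percentages presumes similar time at risk, and nothing in this design makes the times similar.

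Pooling adds a second problem. Reactions to the first infusions arise mainly in subjects who start ublituximab here. Arm A had its first infusions on the parent study, so each Arm A subject adds to the denominator with little chance of adding such an event. Section 4.1 puts everyone on the same regimen, so a table by dose received would mainly separate subjects by umbralisib dose level (Section 6.4.2, Table 5) and leave starters and continuers together.

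Safety of the combination is a stated objective, listed in the synopsis separately for B/C/D and for A. Section 9.8.2 already gives Arm A its own starting point for PFS and duration of response. Section 10 makes no matching provision for safety.

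**Working it through.** The plan states no TEAE rate, sample size or precision target, so there is no figure to reproduce. What follows shows size only. The 52% and the 28-day cycle come from the documents. All hazards, follow-up lengths, Arm A rates and Arm A shares are assumptions.

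1. **Unequal follow-up, same risk.** Crude % = 1 − exp(−λ × cycles).
   - λ = 0.02 per cycle: 6 cycles gives 1 − exp(−0.12) = 11.3%; 24 cycles gives 1 − exp(−0.48) = 38.1%. The ratio is 3.4 with identical risk.
   - The rate is the same for both: 0.02 × 365.25/28 × 100 = 26.1 per 100 patient-years.
   - Over λ = 0.01 to 0.05, the crude figure is 5.8% to 25.9% at 6 cycles and 30.2% to 83.5% at 36 cycles.

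2. **Cohort mix.** Pooled % = (1 − s) × p(starters) + s × p(Arm A), where s is Arm A's share. Section 1.5 reports infusion reactions in 52% of 27 subjects. Take that for starters and assume 0–5% in Arm A.
   - s = 0.25: 39.0% to 0.75 × 52 + 0.25 × 5 = 40.25%
   - s = 0.50: 26.0% to 28.5%
   - s = 0.75: 13.0% to 16.75%
   - If Arm A's rate were 10%, the figure at s = 0.50 would be 31.0%.

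3. **Front-loaded hazard.** Assume 0.08 per cycle for the first six cycles on the combination and 0.01 afterwards.
   - Starters followed 12 cycles: 1 − exp(−(0.48 + 0.06)) = 41.7%.
   - Arm A, already past six cycles, followed 24 more: 1 − exp(−0.24) = 21.3%.
   - Both have the same hazard for a given time on the combination, yet the group followed longer shows the lower figure. Crude percentages can therefore mislead in either direction.

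4. **Limit of a per-year rate.** If 52% react at the first dose and the other 48% are followed T years without the event, the rate is about 0.52/(0.48 × T): 108, 54 and 36 per 100 patient-years at T = 1, 2 and 3. The risk is the same and the rate varies threefold. For such events the percentage in a fixed early window is the stable measure.

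**The case against.** The strongest reply is that this is a descriptive, compassionate-use study with no hypothesis test and no planned safety comparison between arms. Subject percentages are a standard and truthful account of what was seen, and exposure is tabulated as well. Grouping by parent-study arm is already provided for, which would give Arm A its own column.

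Much of this stands. A reader might infer that the planned percentages are invalid or say nothing about risk, and the documents do not support that. What fails is comparison across unequal follow-up, and reading the pooled figure as the combination's incidence. The grouping defence is weaker, because it rests on permissive wording in Section 9.3 and the synopsis while Section 10.1 says something different.

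Three other stronger readings should also be resisted:

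- *Arm A is selected for tolerance.* Section 3.1 requires only non-progression. Tolerance is an inference from continued treatment.
- *Arm A's parent-study events are certainly excluded.* Section 10.4 also counts treatment-related events whatever their start date, and does not say which study's first dose starts Arm A's clock. This is ambiguous.
- *B, C and D form one untreated group to which 52% applies.* Arm C already had ublituximab and, under Section 6.1, has no split first dose or Day 8 and 15 infusions. Arm D already had umbralisib. The 52% comes from 27 subjects of mixed histology (10 CLL/SLL, 9 FL, 7 DLBCL, 1 Richter's) on another ublituximab schedule.

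The objection that patient-year rates do not suit infusion reactions is correct (step 4), and the fix allows for it.

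**Conclusion.** The point holds as a reporting weakness. The only planned TEAE measure ignores time at risk in a study where time at risk is unequal, and no binding rule keeps continuing subjects apart from starting ones. Identical risk can give percentages that differ about threefold (11.3% against 38.1% under the assumed hazard). The pooled infusion-reaction figure could be about half the starters' figure if Arm A is half the study (26–29% against 52%). These sizes are illustrations: the documents do not say which group will be followed longer, how many Arm A subjects will enrol, or what Arm A's event rate will be. Trial conduct is unaffected. What changes is what the safety objective can support.

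**What to change.** - Reconcile Section 10.1 with Section 9.3 and the synopsis so that TEAE tables are by parent-study arm. Show Arm A always separately, as continuing, and B, C and D each separately, as starting, because C and D have already had one component.
- Keep the crude percentages.
- For events that accrue over time, add subjects with a first event per 100 patient-years at risk, counted from first dose on this study to first event or 30 days after last dose. Use the same window for events and person-time, and state whether Arm A's TEAE clock starts at its first dose on this study.
- For front-loaded events such as infusion reactions, give the Cycle 1 percentage by arm instead of a per-year rate, and label Arm A's first cycle here as continued treatment.
- Do not present the pooled percentage as the incidence of the combination.

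**Cost.** Dosing and adverse-event data are already collected, so no new procedure is needed. Tables become slightly longer, and the rate is hard to interpret when the hazard is not constant.
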